To assess how COVID-19 lockdown has changed the dietary habits of participants enrolled in this study. In order to collect this information, we will ask for the participant to complete an online 3-day food record. This part of the study is non-invasive and there will be no in-person contact.

Aim 5 – Exploratory

To assess whether the colonic fermentation modulates gluconeogenesis. Hypothesis: Glucose fermentation induced by lactulose is associated with a drop in gluconeogenesis. Subjects will assume 3ml/ Kg of body water of D2O in three doses *per os* the night before the study and at 7:30 AM they will consume 20g of lactulose. Blood draws will be taken every hour until 8:00 PM. The total blood to be drawn is about 150 ml. The subjects will be allowed to drink during the study, a meal will be served at the end of the study.

We will also collect the breath hourly hydrogen breath test during the study to assess colonic fermentation by measuring hydrogen in the breath. Subjects blow into a small box to collect the breath. There are no risks related to this test.

Aim 6 - Measurement of TCA cycle in vivo in the brain and in the liver by using Deuterium metabolic imaging.

Deuterium metabolic imaging (DMI) is a simple MR-based technique to map metabolism with high temporal and/or spatial resolution. The metabolic fate of deuterated substrates, including glucose and acetate, can be monitored with deuterium MR methods. Recent preliminary data obtained with this protocol suggest that youth with obesity have higher TCA cycle compounds in plasma than lean. This is probably due to an increased metabolic rate related to insulin resistance. To determine if changes observed in plasma mirror metabolic changes in the tissue (brain and liver), we will use a technique that combines stable isotopes and MRI. To measure TCA cycle in the brain we will use 6,6-2H₂-glucose, a compound that has been used for many years in clamp studies, while to measure TCA cycle in the liver we will use D3-Acetate, the compound that we are currently using to measure acetate production (Aim 1 and 3).

TCA cycle measurement in the brain.

To measure TCA cycle measurement in the brain we will infuse 6,6-2H₂-glucose for 2 hours and we will detect the changes in TCA derived compounds in the brain during the infusion. A total of 50 ml of blood will be obtained during this study.

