The labeled glucose is prepared by the Investigational Drug Service of the Yale Pharmacy, as a solution of 20% (w/v) in water. The labeled glucose is infused following a protocol used for decades in the Yale Magnetic Resonance Research Center (MRRC), consisting of a ramp phase followed by a plateau phase. The amount of glucose infused is 0.75g/kg body weight (BW); the volume of glucose solution infused over a 120 min study is 3.6 ml/kg BW.

TCA cycle measurement in the liver.

To measure TCA cycle measurement in the liver we will infuse d3-acetate for 2 hours and we will detect the changes in TCA derived compounds in the liver during the infusion. A total of 50 ml of blood will be obtained during this study.

The labeled acetate is prepared by the Investigational Drug Service of the Yale Pharmacy, as a solution of 350 mM 2H-labeled sodium-acetate in water. The labeled acetate is infused following a protocol used for decades in the Yale MRRC, consisting of a ramp phase followed by a plateau phase. The amount of acetate infused is 0.73g/kg body weight (BW); the volume of acetate solution infused over a 120 min study is 14.2 ml/kg BW.

Calendar of activities for each aim (visits, frequency, assessments, blood draw collection, week number).

Visit number	Frequency	Assessment	Amount of blood to be collected	Week number
AIM 1				
1	once	OGTT	120	1
2	once	Acetate synthesis	94	2
AIM 2				
1	once	DNL assessment	150	3
AIM 3				
1	once	Acetate synthesis	94	4
2	once	Acetate synthesis	94	5
3	once	Acetate synthesis	94	6
4	once	Acetate synthesis	94	7
AIM 4				
1	once	One year follow-up	0	8
AIM 5				
1	once	gluconeogenesis	150	9
AIM 6				
1	once	MRI/Infusion - Brain	50	10
2	once	MRI/Infusion - Liver	50	11

Each visit is one day. If a subject is recruited for more than one aims, then at least 12 weeks will be allowed between the visits

5. Genetic Testing

The genetics portion of the study is optional. Subjects who do not wish to have additional blood drawn for genetic analysis may still have the OGTT. We may wish to contact family members of the subject for the genetic study as well. However, no family member will be contacted without the permission of the index subject, and

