Statistical plan for aim 6. Sample size was estimated with the clinicalcalc online software ([Sample Size Calculator \(clinicalcalc.com\)](https://www.clinicalcalc.com)). Since lactate serves as a precursor of TCA cycle, we based our power calculations on the lactate levels measured during the fasting state in 12 lean and 18 obese children. Based on the mean+/-SD of lactate levels in non-obese group of 0.78+/-0.22 and in the group with obesity 1.023 +/- 0.36, a sample size of 23 subjects per group (46) is needed for an alpha of 0.05 and a power of 95%. Statistical Analyses: Median and interquartile ranges will be calculated. The primary outcome will be TCA cycle after 6,6 D glucose ingestion during the steady state. Non-parametric two sided test will be used to compare TCA cycle between the groups.

SECTION II: RESEARCH INVOLVING DRUGS, BIOLOGICS, RADIOTRACERS, PLACEBOS AND DEVICES

If this section (or one of its parts, A or B) is not applicable, check off N/A and delete the rest of the section.

A. RADIOTRACERS N/A

B. DRUGS/BIOLOGICS N/A

Does the study do any of the following:

Specify the use of an approved drug or biologic?

Use an unapproved drug or biologic?

Use a food or dietary supplement to diagnose, cure, treat, or mitigate a disease or condition? No

This study uses:

13C inulin (labeled) (isotope)
deuterated SCFA/labeled acetate
Deuterium labeled water (heavy water D2O)
6,6-2H2-glucose (isotope)

Lactulose is a dietary supplement that is approved to treat constipation. We will use lactulose to stimulate production of short chain fatty acids by the gut flora.

Cold Isotopes:

FDA allows the use of cold isotopes in research without an IND when certain conditions apply (see below). Confirm that the following are true:

1. *The research is intended to obtain basic information regarding the metabolism (including kinetics, distribution, and localization) of a drug labeled with a cold isotope or regarding human physiology, pathophysiology, or biochemistry.*
2. *The research is not intended for immediate therapeutic, diagnostic, or preventive benefit to the study subject.*
3. *The dose to be administered is known not to cause any clinically detectable pharmacologic effect in humans based on clinical data from published literature or other valid human studies.*
4. *The quality of the cold isotope meets relevant quality standards.*

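### Aim 6 asks whether plasma mirrors brain and liver, but its plan specifies only a lean-versus-obese comparison under the brain tracer: no liver outcome and no plasma-tissue analysis

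*Combined protocol and SAP*

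**What the plan says.** Section I, item 4 (Research Plan), Aim 6, starts from a preliminary finding that "youth with obesity have higher TCA cycle compounds in plasma than lean". It then gives the purpose: "To determine if changes observed in plasma mirror metabolic changes in the tissue (brain and liver), we will use a technique" combining stable isotopes and MRI.

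Two tracers are assigned, one per organ. For the brain, "we will infuse 6,6-2H₂-glucose for 2 hours". For the liver, "we will infuse d3-acetate for 2 hours and we will detect the changes in TCA derived compounds in the liver during the infusion". Each study draws 50 ml of blood, and the calendar of activities lists the brain and liver sessions as separate Aim 6 visits.

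Section I, item 13, Statistical plan for aim 6, contains:
- a sample size of 23 per group (46 in total), based on fasting lactate in 12 lean and 18 obese children;
- medians and interquartile ranges;
- one endpoint: "The primary outcome will be TCA cycle after 6,6 D glucose ingestion during the steady state";
- one two-sided non-parametric test of TCA cycle between the groups.

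It names no acetate-tracer or liver outcome, no plasma TCA variable, and no correlation, regression or agreement analysis. No other section supplies them.

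**The concern.** The objective relates two kinds of measurement, plasma and tissue, in two organs. The plan specifies one kind of measurement in one organ. A group difference in brain TCA activity is relevant, but obese youth can be higher in plasma and higher in brain for unrelated reasons. The group test alone therefore cannot show that plasma follows tissue.

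Two things are at stake. First, a two-hour liver infusion visit with 50 ml of blood feeds no specified result, in a study that its own safety section rates as greater than minimal risk. Second, if investigators want to comment on mirroring or on the liver, the compound, time point and method will be chosen after the data are seen.

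**Working it through.** **1. Objective and plan side by side**

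| Element of the objective (Research Plan, Aim 6) | Counterpart in the statistical plan for aim 6 |
|---|---|
| Brain TCA, glucose tracer | Primary outcome, compared between groups |
| Liver TCA, acetate tracer | None specified |
| Plasma TCA compounds | None specified |
| Plasma in relation to brain | None specified; addressed indirectly by the group test |
| Plasma in relation to liver | None specified |

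The protocol does plan for a question of this kind elsewhere. Aim 2 asks whether SCFA synthesis modulates lipogenesis, and item 13 regresses one on the other.

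**2. The plan's own sample size**

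Inputs (statistical plan for aim 6): means 0.78 and 1.023, difference 0.243; SDs 0.22 and 0.36; two-sided alpha 0.05; power 95%.

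- With the lean SD in both groups: n = 2 × [0.22 × (1.960 + 1.645) / 0.243]² = 21.3, so 22 per group. The t-based version gives 22.3, so 23. The stated figure is reproduced.
- With both stated SDs: n = (0.22² + 0.36²) × (3.605 / 0.243)² = 39.2, so 40 per group. At 23 per group, t-test power is then about 77%.

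This is a side point. It matters here only because it shows how little room there is to divide alpha between two organs: at 0.025 the same calculation gives about 67%. Testing both organs at 0.05 with no hierarchy would, if the tests were independent, give a familywise error of 1 − 0.95² = 0.0975.

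**3. What a shared group difference implies about tracking (illustration)**

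Assumptions not in the documents: plasma and tissue TCA measures each differ between groups by the lactate gap, and within groups they are uncorrelated.

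- Standardised difference d = 0.243 / √[(0.22² + 0.36²)/2] = 0.243 / 0.298 = 0.81.
- Pooled correlation produced by group alone, equal groups: (d²/4) / (1 + d²/4) = 0.166 / 1.166 = 0.14.

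So the planned brain test could well be positive when plasma says nothing about an individual's tissue value beyond group membership.

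**4. What a plasma-tissue analysis could deliver with the planned subjects**

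Fisher z, 46 subjects with both measures, one covariate (group): SE = 1/√(46 − 3 − 1) = 1/√42 = 0.154. Then 1.96 × 0.154 = 0.302, which back-transforms to a half-width of 0.29 at r = 0. Inflating the variance by 1.06 for Spearman gives 0.30.

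| Observed r | Approximate 95% CI |
|---|---|
| 0 | −0.29 to 0.29 |
| 0.3 | 0.01 to 0.55 (0.00 to 0.55 with the Spearman adjustment) |
| 0.6 | 0.37 to 0.76 |

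The intervals at 0 and 0.6 do not overlap. A moderate value such as 0.3 would be inconclusive. If only 23 subjects contributed to an organ, SE = 1/√19 = 0.229 and the half-width at zero is about 0.42.

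**The case against.** The best defence is that mirroring is meant at group level. The only plasma change described is obese against lean, so the natural question is whether the same gap appears in tissue. On that reading the brain comparison is responsive: a brain difference would be consistent with mirroring, and no difference would count against it. This stands. A reader might infer that the objective is within-person agreement and that the planned test therefore has no bearing on it. The documents do not support that, because they mention neither agreement nor a within-person comparison.

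A reader might also infer that the liver data are excluded from analysis. That goes too far. The plan names a primary outcome, not a sole one, and its test sentence refers to TCA cycle in general. A liver comparison is unspecified rather than ruled out.

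The numerical illustration also has limits. It borrows a fasting-lactate gap for TCA measures and assumes no within-group correlation. The pooled correlation of 0.14 is not something the plan proposes to calculate.

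None of this fills the gap. Even on the group-level reading, the objective names the liver, the plan gives it no outcome, and plasma TCA is not an endpoint anywhere in the aim.

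**Conclusion.** The concern holds in this form: as specified, Aim 6 answers at most a group-level question about brain. It does not specify how liver will be assessed or how plasma will be set against tissue in either organ. This should be corrected by amendment. It does not invalidate the brain comparison.

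The mismatch itself rests on the text alone. The figures are illustrative: about 0.14 for the correlation due to group alone, and a half-width of about 0.3 for the added analysis. The second assumes that all 46 subjects complete both sessions and that plasma TCA compounds can be assayed in the blood drawn. The documents state neither; they do not say what the 50 ml samples are for.

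A separate wording conflict needs attention. The statistical plan speaks of the glucose tracer being ingested, while the Research Plan describes an infusion. The two passages must be reconciled.

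**What to change.** 1. Name two tissue outcomes: brain TCA labelling in the glucose-tracer session and liver TCA labelling in the acetate-tracer session, each compared between lean and obese. State the hierarchy, for example brain primary and liver secondary, so that alpha is not split.
2. For each organ, add an association across subjects between plasma TCA compounds and the tissue measure from the same session, adjusted for group (partial Spearman with 95% CI). Describe it as a between-subject association; one plasma and one tissue value per person per session does not measure within-person agreement. Fix the compounds and time point in advance.
3. Base any statement that plasma mirrors tissue on that estimate together with the group comparisons, and say beforehand that 46 subjects can separate only strong from absent association.
4. Confirm that the session blood can be used for plasma TCA assays and that participants are expected to attend both sessions.
5. Reconcile the ingestion and infusion wording.

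The cost is protocol wording, an extra assay and analysis, and one more outcome in the hierarchy. If the assumptions in step 4 hold, no new visits are needed.
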